3.3 Study Duration, Enrollment and Number of Sites

3.3.1 Duration of Study Participation

Enrollment for this study will last 18 months (starting on August 7, 2018 and ending on February 7, 2020). When a subject is enrolled, their first home visit will be within four weeks of their enrollment. Each phase lasts four weeks, but it is possible there will be delays of up to four weeks between phases for some participants. Therefore, for each subject, we expect to have all of our data for both phases 16 weeks from the date of enrollment at the latest. We expect the study to be complete by the beginning of February of 2020 at the latest.

Expected time commitment for parents and subjects for each phase can be found in tables 1 and 2 on pages 4-6.

3.3.2 Total Number of Study Sites/Total Number of Subjects Projected

There will be 10 sites for this study. Each site is an operating public school, private school, therapy center, therapist practitioner, or research organization where a therapist practitioner provides regular treatment for children with autism or regularly conducts research involving children with autism. Therefore, we expect to potentially enroll up to 150 subjects.

3.3.3 Offer of Free BioStream Training and Follow-up Study to Control Group

If funding permits, at the end of Phase II of the study, the study Sponsor would like to invite all participants in the control group (alternate game group) to participate in the BioStream Training. The study team will collect performance data on these participants over the course of 2 months. The study PI will submit a detailed protocol amendment to the IRB for approval prior to enrolling any of the control group participants in this study. Participant permission to be contacted regarding this additional part of the project is included in the consent form attached to this IRB package.

3.4 Study Population

3.4.1 Inclusion Criteria

- 1) Parental/guardian permission (informed consent) and if appropriate, child assent.
 - 2) The parent who participates in the screening, completes the questionnaires, and provides informed consent must be proficient in English.
 - 3) Age 4 years 0 months up to 14 years, 11 months, and 29 days.
 - 4) English as the child's primary/first language (the intervention does not currently have alternate language versions).
 - 5) Capable of using a handheld video game controller (as reported by parent).
 - 6) Has successfully played a video game using a Microsoft Xbox game controller, Sony PlayStation game controller, or other comparable game controller.
 - 7) Parent reports AT LEAST ONE of the following:
 - a) Score of ≤ 2 on a modified version of Question 15 of the Social Responsiveness Scale (SRS) ("Is able to understand the meaning of other people's facial expressions.")
 - b) Score of ≥ 2 on a modified version of Question 16 of the Social Responsiveness Scale (SRS) ("Avoids eye contact.")
 - 8) Confirmed diagnosis of ASD from a licensed medical professional.
-

- 9) Estimated intelligence standard score of at least 40 (can be substituted for a receptive language score such as PPVT or use of the Differential Ability Scales, 2nd Edition (DAS-II)).
- 10) Attains a score equal to or less than 75% correct on the Ekman 60 Faces Test.

3.4.2 Exclusion Criteria

- 1) History of seizures.
- 2) History of traumatic brain injury or other significant medical or neurological abnormality affecting motor or higher cortical functioning. This includes gestational age below 32 weeks or perinatal injury, where the risk for brain injury is greatly increased. Rationale: a primary aim of the study is to identify sequences in our game-like applications that are appealing to youth with ASD; it is not clear that individuals with any type of acquired brain injury would provide useful data on what appeals to an individual with ASD.
- 3) A visual disorder that cannot be corrected through the use of corrective lenses to a level of 20-40 in both eyes.
- 4) Use of corrective visual lenses that would significantly impede the valid collection of visual attention and gaze pattern data during dyadic interaction tasks.
- 5) Auditory impairment (that cannot be corrected by a hearing aid) that would significantly impede the valid collection of test measures.
- 6) Profound intellectual disability or sensory-motor difficulties that would preclude valid use of diagnostic instruments and/or use of a computer or mobile computing device.
- 7) A DSM 5 disorder or other psychiatric symptoms that would interfere with the participant's ability to participate in the study (e.g., active psychosis), per parent report.
- 8) History of one or more psychiatric hospitalizations.
- 9) Presence of significant symptoms of a conduct disorder.

Subjects that do not meet all of the enrollment criteria may not be enrolled. Any violations of these criteria must be reported in accordance with IRB Policies and Procedures.

4 STUDY PROCEDURES

4.1 Initial Screening

See section 3.1.1 for a full description of the initial screening.

4.2 In-Person Study Visits

During the in-person study visits, parents and subjects will complete the following assessments, described in section 1.4 unless otherwise noted. Tables 1 and 2 also show details on the schedule of all in-person assessments for both phases.

Social Responsiveness Scale – Parent (SRS) – 10 minutes, parent only (may be administered by phone).

Childhood Joint Attention Rating Scale (C-JARS) – 10 minutes, parent only (may be administered by phone).

Dyadic Interaction Task – 10 minutes, subject only.

Eye Tracking Video Assessment – 10 minutes, subject only.

Ekman 60 Faces Test – 10 minutes, subject only.

Emotional Expression Video Assessment – 10 minutes, subject only.

Test of Variables of Attention (TOVA) – 22 minutes, subject only.

An introduction to game and equipment (Only Phase I Visit 1) – 40 – 60 minutes, with the parent/guardian, teacher, or therapist.

Subject Interview/Survey (described in section 5.4.1) – 10 minutes, subject only.

Parent/Teacher/Therapist Interview/Survey (described in section 5.4.2) – 10 minutes, parent, teacher, or therapist only.

Video Recording of Study Visits: All study team member visits to the home, school, or therapy center may be video recorded using a single or multiple video cameras and tripods.

Please note that for subjects who are using the BioStream Training in their school, therapy center or research organization, their parent/guardian only needs to be present for the first visit. After that visit, surveys involving the parent including the Social Responsiveness Scale and Childhood Joint Attention Rating Scale can be conducted over the phone.

4.3 Subject Completion/Withdrawal

Study participants may withdraw from the study at any time. They may also be discontinued from the study:

- 1) For failing to meet all inclusion criteria.
 - 2) For meeting an exclusion criterion.
 - 3) For not adhering to scheduled visits (at the discretion of the PI).
 - 4) For failing to comply with study requirements (at the discretion of the PI).
 - 5) For reasons of safety or for administrative reasons (at the discretion of the PI).
 - 6) If the participant is otherwise not well-suited for further participation in the study (at the discretion of the PI).
-

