All written or electronic forms (except Informed Consent Forms and Assent Forms) will employ a unique alphanumeric identifier; in no case will the participant's name or other identifying information appear on these forms. The user ID for the BioStream Training and alternate game shall use the same unique alphanumeric identifier. The study team will accomplish this on all parent/guardian or teacher or therapist questionnaires (as applicable) which have lines for child and parent name by applying a label with unique alphanumeric identifier and instructing parents/guardians or teacher or therapists to use generic labels (e.g., biological mother) rather than writing their names. The PI will keep a master list containing PHI and subject ID number separate from coded data forms, which will be maintained in a locked file drawer, cabinet, or lock box in the PI's office. Only the PI will have access to this location. The master list will be maintained on a separate password-protected computer and be stored in an encrypted password protected file. Video recordings will stored on password-protected and/or encrypted data storage devices including computers, external hard drives, and/or flash drives only accessible by members of the study team.

**TABLE 1: SCHEDULE OF STUDY PROCEDURES
(INITIAL SCREENING)**

| | Estimated time | Parent or subject? |
|---|-----------------------|---------------------------|
| Informed Consent | 15 minutes | Parent |
| Review of Inclusion/Exclusion Criteria (Initial Screening Interview) | 15 minutes | Parent |
| Video Game Interview Form (Parent-Report) | 15 minutes | Parent |

**TABLE 2: PHASE I SCHEDULE OF STUDY PROCEDURES
(HOME, SCHOOL, THERAPY CENTER, OR RESEARCH ORGANIZATION)**

| | Estimated time (total over all visits) | Parent or subject? | Visits applicable (Total 6 Visits) |
|--|---|---------------------------|---|
| Informed Consent/Assent (if applicable) | 30 minutes | Parent and subject | Visit 1 |

| | | | |
|---|----------------------------------|----------------|--|
| Peabody Picture Vocabulary Test (PPVT) | 20 minutes | Subject | Visit 1 |
| Ekman 60 Faces Test | 10 minutes | Subject | Visit 1 |
| SRS (Parent-Report) | 50 minutes | Parent | Visits 2-6 |
| C-JARS (Parent-Report) | 50 minutes | Parent | Visits 2-6 |
| Dyadic Interaction Task | 50 minutes | Subject | Visits 2-6 |
| Eye Tracking Video Assessment | 50 minutes | Subject | Visits 2-6 |
| Ekman 60 Faces Test | 50 minutes | Subject | Visits 2-6 |

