Sponsor may provide a web interface for password protected access by any or select members of the study team that shows and/or permits the download of, subject de-identified study data using secure channels which may include secure FTP or HTTPS. The Sponsor may electronically send to any member of the study team reports containing subject de-identified study data. The Sponsor may otherwise electronically communicate subject de-identified study data to any member of the study team. The communication of this de-identified study data to any member of the study team will facilitate monitoring for compliance and data integrity in a real-time fashion.

Sponsor may notify any member of the study team about any subject ID numbers that failed to play the intervention or the alternate game over any 24-hour period. Any member of the study team may reach out to subjects and/or parents and teachers or therapists (as applicable) to remind them to play (by phone, email, and/or text message). Subjects will also have the opportunity to contact any or select members of the study team through phone or email if any questions arise.

The Sponsor may, from time to time, transmit updates to the software installed on the Subject Computer using the communication link described above.

Alternate Comparison Game:

The BioStream Training is being compared to a modified version of the BioStream Training, which will not include the same therapeutic exercises. The game will be played by subjects in the non-intervention group for the same length of playing time and at the same frequency,

as the BioStream Training intervention group. It will require a similar game controller device as that which is used by the intervention group and will be computer based. The Sponsor may also use as the alternate comparison game any video game that is rated E (Everyone) by the Entertainment Software Rating Board.

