3.1.1 Initial Screening

Potential subjects will be first screened by any study team member in an in-person or telephone interview with the parent/guardian. After written informed consent is obtained to the initial screening (in the case of an in-person interview) or verbal informed consent is obtained to the initial screening (in the case of a telephone interview), protocol inclusion and exclusion criteria will be reviewed with the parent/guardian. The parent/guardian will also be asked for a list of the medications the subject is currently taking and that information will be recorded. A subset of questions from the SRS will be asked as part of the screening. The parent/guardian will also be asked if the subject has a diagnosis of ADHD and if so, that will be noted.

Prospective Study Participant Initial Screening Form. This short questionnaire will be administered to the parent/guardian in-person or by telephone prior to the study visit to

query their children's video game playing habits. This questionnaire should take less than 15 minutes to complete. Questions related to the inclusion/exclusion criteria will also be asked to determine eligibility.

3.1.2 Phase I Visit 1

Parental/guardian permission (informed consent) and, if applicable, child assent, will be obtained. Subjects will participate in social skills assessments. The subject will participate in the Peabody Picture Vocabulary Test, 4th Edition [34]. If the study team member determines that the subject's intelligence standard score is below 40, then the subject will not be able to continue to be included in the study per the exclusion criteria (see page 4). The subject will participate in the Ekman 60 Faces Test. If the subject score is greater than 75% correct, then the subject will not be able to continue to be included in the study per the exclusion criteria.

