5.7.2 Efficacy Analysis

The primary analysis will be based on all subjects randomized at the initial visit for who initial visit and final visit data is collected.

Paired-sample t-tests will be used to measure changes from baseline within each group, and independent sample t-tests will be used to measure changes from baseline relative to the alternate game group for all endpoints.

For all endpoints, we will determine whether there were statistically significant changes in scores from baseline or relative to the alternate game group. Significance will be set at $p < 0.05$. Multiplicity of primary endpoints will be managed via statistical corrections.

Secondary endpoints will be evaluated in a similar manner. Analysis will include all subjects for who initial visit and final visit data is collected. The treatment and control groups will be compared using t-tests as described above.

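### Section 4.3 lets the PI discontinue randomised children from the study for missed visits, non-compliance or unsuitability; with a completers-only analysis, behaviour after randomisation can decide who is analysed

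*Combined protocol and SAP*

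**What the plan says.** Protocol section 4.3 lists six grounds on which a participant may be discontinued from the study. Three concern conduct or suitability after entry, and each is left to the PI:

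- Item 3: not keeping to scheduled visits.
- Item 4: "For failing to comply with study requirements (at the discretion of the PI".
- Item 6: "If the participant is otherwise not well-suited for further participation in the study (at the discretion of the PI".

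Section 4.3.1 is titled as an early termination visit. It contains only voluntary exit interviews with the child and the parent, and it describes them for a child who chooses to leave. It schedules no outcome assessment.

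Section 5.7.2 defines the analysis set: "The primary analysis will be based on all subjects randomized at the initial visit for who initial visit and final visit data is collected". The same restriction is stated for the secondary endpoints. The Supplement to the SAP adds mixed ANOVAs for three scales but sets no different analysis population.

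Section 3.2 has blinding in its title, but its text covers random assignment only. The only people the protocol describes as blinded are those who annotate the dyadic-task videos (sections 1.1, 1.4 and 7.3). Section 1.2 says that sending play data to the study team "will facilitate monitoring for compliance and data integrity in a real-time fashion".

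**The concern.** Randomisation protects the comparison only if membership of the analysis set does not depend on what happens afterwards. Here a judgement about conduct during the trial can take a child out of the study, and the analysis rule then takes the child out of the comparison. No compliance standard anchors that judgement: section 1.3 gives a ceiling on sessions (20, on at most five days a week) and a range of session length (20 to 100 minutes), but no minimum number of sessions.

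Children who play little or miss visits may well be those who would have changed least. If more of them are removed from the BioStream arm, its mean change is flattered. If more are removed from the alternate-game arm, the comparison is biased against BioStream. Engagement could differ by arm, because sections 1.2 and 3.1 let the comparator be either a modified version of the training or any game with an E rating.

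**Working it through.** **Step 1. Follow one child through the text.**

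1. A randomised child plays little. Item 4 permits discontinuation from the study, and no threshold is given.
2. Section 4.3.1 schedules no outcome assessment for that child. For a child removed by the PI, as opposed to one who leaves, it does not even describe an interview.
3. The child has no final-visit data. Scores from intermediate visits do not count as final-visit data under 5.7.2.
4. The child is therefore outside both the primary and the secondary analysis.

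The chain needs 4.3, 4.3.1 and 5.7.2 together. Section 4.3 alone does not define the analysis set.

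**Step 2. Is there a planning figure to reproduce?** No. Section 5.8 gives only a maximum of 150 participants, with no effect size, SD, power, allocation ratio or dropout rate. What follows is an illustration on assumed inputs.

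**Step 3. Illustration.** Assumptions: 75 per arm (150 split equally), no true effect, change scores with SD 1, a two-sided test at 0.05 without multiplicity correction, and removed children who would have changed g = 0.5 to 0.8 SD less than those retained in their arm.

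If a fraction q of an arm is removed, the full-arm mean is (1 − q)m + q(m − g) = m − qg, where m is the mean of those retained. Analysing only the retained children therefore shifts that arm by qg. With fractions q1 and q0 removed from the two arms:

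- shift = (q1 − q0) × g
- noncentrality = shift / √(1/n1 + 1/n0), where n = 75(1 − q) in each arm
- the false-positive rate is the two-sided rejection probability of the noncentral t with n1 + n0 − 2 degrees of freedom.

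| Removed (one arm vs other) | g | n1, n0 | Shift (SD) | Noncentrality | False-positive rate |
|---|---|---|---|---|---|
| 10% vs 0% | 0.5 | 67.5, 75 | 0.10 × 0.5 = 0.05 | 0.298 | 6.0% |
| 20% vs 0% | 0.8 | 60, 75 | 0.20 × 0.8 = 0.16 | 0.924 | 15.1% |
| 20% vs 10% | 0.5 | 60, 67.5 | 0.10 × 0.5 = 0.05 | 0.282 | 5.9% |
| 20% vs 10% | 0.8 | 60, 67.5 | 0.10 × 0.8 = 0.08 | 0.451 | 7.3% |
| equal | either | equal | 0 | 0 | 5.0% |

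**Step 4. Cross-check with a different model.** Remove the least compliant fraction q of one arm, with an assumed correlation ρ of 0.3 to 0.5 between compliance and change. The expected bias is ρφ(z_q)/(1 − q). For q = 20% and ρ = 0.3 this is 0.3 × 0.280 / 0.80 = 0.105 SD. Simulation with 20,000 runs and 75 per arm gave these false-positive rates:

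- q = 5%: 5.4% to 6.5%
- q = 10%: 6.6% to 9.4%
- q = 20%: 9.7% to 17.8%
- the same removal in both arms: bias about zero, 4.9% to 5.9%

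Both models agree that the harm comes from removal that differs between arms.

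**The case against.** **This is ordinary discretionary wording, and removal may be rare.** Items 3, 4 and 6 are permissive. The response to missed play described in section 1.2 is a reminder by phone, email or text, not removal. This is fair, and it makes high removal rates less likely. It does not close the route, because nothing in 4.3 limits how often the grounds are used.

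**Both arms face the same rules.** They play for the same time at the same frequency, and equal removal causes almost no bias. This stands, so the one-arm figures are an upper illustration and the 20% versus 10% case is milder. The plan offers no reason to expect equal removal, however.

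**The fault lies in 5.7.2.** In part it does. But widening the analysis set alone would not help, because a discontinued child would still have no final assessment.

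**The planned multiplicity correction is ignored.** The figures do use an uncorrected 0.05, because the correction is not specified. A correction would lower each test's threshold but would not remove a shift in the mean.

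Two stronger readings are tempting, and the documents do not support either.

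- *The PI is unmasked.* The plan is silent. Study-team members train families on the assigned game and may see play data by subject identifier, but no section says that the PI knows the allocation or that those reports show it. The supportable statement is that masking of the PI is not stated.
- *Item 1 would remove children whose Ekman score improves.* Item 1 reads "For failing to meet all inclusion criteria" and the entry criterion reads "Attains a score equal to or less than 75% correct on the Ekman 60 Faces Test". Neither carries a time limit, and the test is repeated as an outcome at Visits 2 to 6. But section 3.1.2 applies the cut-off at Phase I Visit 1: "If the subject score is greater than 75% correct, then the subject will not be able to continue to be included in the study". No section applies it later, and change on this test is a primary endpoint. Eligibility at entry is the natural meaning. At most this is a sentence to clarify.

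**Conclusion.** The point holds. Items 3, 4 and 6 of section 4.3, read with 4.3.1 and 5.7.2, allow conduct after randomisation to determine who enters the efficacy comparison. The decision has no stated threshold and is made by a PI whose masking is not stated.

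The size is uncertain, because the documents give no removal rate or SD. On the assumptions in the working, the false-positive rate ranges from about 5% (equal removal), through about 6% to 7% (20% versus 10%), to about 6% to 15% (10% to 20% from one arm only). Without differential removal there is almost no bias. This is a cheap improvement worth making. It does not show that the comparison will be biased.

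**What to change.** In section 4.3:

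1. Reword items 3, 4 and 6 so that they may end game sessions but not outcome follow-up. The child stays in the study and the final assessment is still scheduled unless consent is withdrawn.
2. State there and in 5.7.2 that such children are analysed in their assigned arm whatever the amount of play.
3. Report discontinuations by arm, ground and date.
4. Optionally, add to items 1 and 2 one sentence saying that eligibility is judged once, on screening and Visit 1 data.

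No safety or session-stopping rule is altered; item 5 and section 6.2 stay as they are.

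The cost is protocol wording, plus staff time for some final visits that are already in the schedule. The observed effect may be somewhat smaller because low players remain in the comparison.

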4.3.1 Early Termination Study Visit

Subject Exit Interview/Survey

In the case that a subject decides to leave the study early, the subject will be asked to complete a final interview. This interview will discuss the reasons for leaving the study, will be completely voluntary, and may be discontinued at any time during the interview by the subject.

Parent Exit Interview/Survey

In the case that a subject decides to leave the study early, the parent/guardian will also be asked to complete a final interview. This interview will discuss the reasons for the subject leaving the study, will be completely voluntary, and may be discontinued at any time during the interview by parent/guardian.

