6.2 Adverse Event Reporting

If, at any time, during any BioStream Training session or play of the alternate game session, the parent/guardian or teacher or therapist (as applicable) observes the subject displaying seizure symptoms, or becoming agitated, frustrated, disturbed, or in any other manner being negatively impacted (including in a manner that may pose a risk to the subject's safety or well-being or the safety or well-being of others) or in their judgment, believes the subject will or may become negatively impacted in any way (including in a way that may pose a risk to the subject's safety or well-being or the safety or well-being of others), they will immediately discontinue the session, stop the subject from engaging in any further sessions, and contact the Principal Investigator to inform him or her of this occurrence. AEs that are not serious but that are notable and could involve risks to subjects will be summarized in narrative or other format and submitted to the IRB at the time of continuing review.

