7.7 Payment to Subjects/Families

7.7.1 Compensation

As compensation for time and expenses, child participants will be provided with a gift card upon the completion of each phase of the study. The total value of each gift card provided to each subject over the course of this study will not exceed \$50 per completion of each phase of the study. Gift cards may be for retailers such as Amazon and Target. In addition, each study participant will be provided with a gift card not to exceed \$5 to retailers such as Amazon and Target for each time he or she completes the TOVA assessment.

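### No outcome assessment is planned at or after an early stop, and the completer rule then discards the weekly outcomes of every child without a final visit

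*Combined protocol and SAP*

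**What the plan says.** Section 4.3.1 is headed as a study visit but contains only two interviews, one with the child and one with the parent. The trigger is the child's own decision: "In the case that a subject decides to leave the study early, the subject will be asked to complete a final interview". The content is reasons only: "This interview will discuss the reasons for leaving the study, will be completely voluntary". No outcome measure is listed.

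There are other ways to stop. Section 4.3 lists six grounds for discontinuation, four of them at the PI's discretion, and describes no exit contact for any of them. Under section 6.2, an adult who sees a child negatively affected must stop the session and "stop the subject from engaging in any further sessions". Neither that section nor any other says whether the child then stays in the study and attends the remaining visits.

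Section 5.7.2 sets the analysis population: "The primary analysis will be based on all subjects randomized at the initial visit for who initial visit and final visit data is collected". The secondary endpoints follow the same rule. No method for missing data is given. The supplement of April 25, 2022 adds a pre/post mixed ANOVA for Ekman, SRS and C-JARS. That analysis also needs a post value, and the supplement does not say what happens when there is none.

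On payment, section 7.7.1 says that "child participants will be provided with a gift card upon the completion of each phase of the study". It adds a card of up to $5 for each completed TOVA.

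**The concern.** Randomization protects the comparison only among the children who are analysed. A completer rule keeps that protection if stopping is unrelated to outcome, or is related in the same way and to the same extent in both arms. Neither can be assumed here. Section 6.2 stops play on agitation, frustration or disturbance, which may well go with a poorer result. The two games also differ in content: section 1.2 says that the comparison game leaves out the same therapeutic exercises. The arms could therefore lose different numbers or kinds of children, and the result would describe children who tolerated their game rather than all children randomized.

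Two features of the plan combine to produce this. Section 4.3.1 does not seek the endpoint value once a child has stopped. Section 5.7.2 then ignores the values collected before the stop.

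**Working it through.** **1. What is collected before a stop.** Dividing the total minutes in Tables 2 and 3 by the minutes per visit in section 4.2 gives the number of assessments per measure.
- Phase I: 50/10 = 5 (TOVA 109/22 = 4.95). That is the Visit 2 baseline plus four weekly sets at Visits 3 to 6.
- Phase II: 40/10 = 4 (TOVA 87/22 = 3.95). That is one set at each of the four visits.

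**2. What the completer rule discards.** The number of post-baseline sets a child has on leaving depends on the last visit attended.

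| Last visit attended | Post-baseline sets held |
|---|---|
| Phase I Visit 2 | 0 |
| Phase I Visit 3, 4, 5 | 1, 2, 3 |
| Phase II Visit 1, 2, 3 | 4 + 1 = 5, 4 + 2 = 6, 4 + 3 = 7 |

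The sets in the second row go unused under 5.7.2. The third row depends on which visit is final. If it is Phase II Visit 4, up to seven sets are discarded. If it is Phase I Visit 6, the child stays in. Section 5.7.2 does not name the phase.

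**3. Possible size of the bias.** The documents state no stop rate, effect size, SD or dropout allowance (5.8 gives only up to 150 children), so there is no figure of the plan's to reproduce and every input here is an assumption. Let a share p of an arm stop, and let stoppers change by d SD less than stayers. The true arm mean is then (stayers' mean) − p × d, so the completer mean overstates it by p × d. The between-arm bias is the difference of these terms.

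| Loss, BioStream vs control | d | Same d in both arms | d in BioStream arm only |
|---|---|---|---|
| 20% vs 10% | 0.5 | 0.20×0.5 − 0.10×0.5 = 0.05 SD | 0.20×0.5 = 0.10 SD |
| 30% vs 10% | 0.8 | 0.30×0.8 − 0.10×0.8 = 0.16 SD | 0.30×0.8 = 0.24 SD |

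If the control arm has the larger loss, the signs reverse.

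**4. What that does to a test.** Assume further 75 per arm (the allocation ratio is not stated), SD 1, no true effect, one endpoint and a two-sided 5% test.
- 30% vs 10%: 75×0.7 = 52.5 and 75×0.9 = 67.5 remain. SE = √(1/52.5 + 1/67.5) = 0.184. Biases of 0.16 and 0.24 SD are 0.87 and 1.30 SE, and the false-positive rate is P(|Z + shift| > 1.96) = 14% and 26%.
- 20% vs 10%: 60 and 67.5 remain. SE = √(1/60 + 1/67.5) = 0.177. Biases of 0.05 and 0.10 SD are 0.28 and 0.56 SE, and the rate is 6% and 9%.

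**The case against.** The strongest reply is that the plan already collects a good deal from children who stop, and that several stronger readings fail.

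- **That no outcome is taken from a child who stops early.** A reader of 4.3.1 alone might infer this. Tables 2 and 3 contradict it: every primary and secondary measure is scheduled at each weekly visit, and only a child who leaves before Phase I Visit 3 has no post-baseline value.
- **That every child who stops leaves the efficacy analysis.** The text does not go that far. Section 6.2 ends play, not visits, and a child who still attends the final visit is analysed. A child who leaves during Phase II may also be analysable, depending on which visit is final.
- **That analysis cannot help afterwards.** It can in part, because the weekly values can enter a longitudinal model under a stated missing-data assumption.
- **That families have no reason to return.** The TOVA card does not depend on completing a phase, and 7.7.1 does not say that completing a phase requires continued play.
- **That the BioStream arm will lose more children.** Section 7.4.2 attributes frustration, anxiety and stress to both games. Its remark on challenging social interactions follows a sentence about the length of the assessments, which both arms undergo. Greater loss in one arm is a possibility, not something the protocol states.
- **That reasons go unrecorded after a 6.2 stop.** They are partly covered, since the adult must inform the PI.

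All of this stands and narrows the point. It does not remove it. The planned analysis does not use the weekly values. A model that did would still have to assume that children who stopped would have continued like comparable children who stayed, and only final values from some of those who stopped can test that.

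**Conclusion.** The point holds in this form: no outcome is planned at or after an early stop, no follow-up is described for stops by the PI or under 6.2, and 5.7.2 drops each child without final-visit data along with the weekly outcomes already held. The comparison is therefore open to bias from selective loss.

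The documents fix neither the size nor the direction. The range of 0.05 to 0.24 SD rests wholly on the assumed stop rates and assumed differences between stoppers and stayers, and 0.24 SD is the upper scenario. With little loss, or with loss unrelated to outcome, the bias would be negligible. This is a weakness that should be mended because mending it is cheap, not evidence that the trial's result is wrong.

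**What to change.** **(a) Section 4.3.1.** State that stopping the game does not by itself end study participation. Unless consent or assent is withdrawn, child and parent are still asked to complete the phase-end assessments (Phase I Visit 6, Phase II Visit 4), whoever made the decision to stop. Where they will not return, offer the existing measures at the termination contact, with SRS and C-JARS by phone as the minimum (section 4.2 already allows this) and the child's tests only if the child is willing.

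**(b) Section 5.7.2.** Name the phase whose last visit is the final visit for the primary endpoint. Analyse all randomized children who have a baseline and any post-baseline value with a repeated-measures model that includes the weekly assessments, and keep the completer t-test as a sensitivity analysis. Report by arm how many children have no post-baseline value, since this model leaves them out.

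**(c) Sections 4.3, 6.2 and 7.7.1.** Record the reason for stopping for 6.2 stops and PI discontinuations as well, and state that attending the phase-end assessment counts as completing the phase for the gift card.

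The rule for when a child's sessions are stopped is unchanged.

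**Cost.** A few sentences of amendment and no new instrument. Some families will decline, some children may find the extra assessment tiring (7.4.2 acknowledges fatigue and stress from assessment length), and a few more gift cards are paid. One limit is timing. The 2022 supplement reports the Ekman ANOVA as already done, so for children whose follow-up has ended only (b) can still be applied, and it should be labelled as added after that analysis.
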